10.2.1 Celecoxib Non-Hematologic Toxicities

Considered to be possibly, probably, or definitely related to Celecoxib (Interferon Alpha-2b and rintatolimod will be continued). See Table 2. Celecoxib will be discontinued for any attributable grade ≥ 2 toxicity, except for nausea, vomiting, or a similar readily manageable condition.

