10.2 Dose Modification

The following dose modification rules will be used with respect to potential toxicity. Toxicity will be assessed according to the NCI Common Terminology Criteria for Adverse Events Version 5.0 (CTCAE v5.0).

Therapy will be immediately discontinued for any grade IV treatment-related toxicity that becomes apparent. The exception to this is for grade 4 neutropenia of $<$ 7 days duration. Study treatment will be reinitiated for any grade treatment-related III toxicity pending the reversal of such toxicity after withholding treatment (i.e. the toxicity resolves to the subject's baseline level). In the event of any adverse effect, appropriate medical treatment will be instituted and study treatment will be discontinued if the above toxicity remains.

PROTOCOL TITLE: Phase 2A Study Evaluating a Chemokine-Modulatory Regimen in Patients with Colorectal Cancer Metastatic to the Liver

Table2. Treatment Related Toxicity Management

Treatment-related AEs	Toxicity grade or conditions (CTCAE5.0)	Action taken for Interferon Alpha-2b	Action taken for Rintatolimod	Action taken for Celecoxib	Additional actions
Chills/Fever	Grade 3	None	None	None	Consider additional acetaminophen dosing, supportive care
Pancreatitis	Grade 3	Hold Decreased future doses by 50%	Hold	Hold	Supportive measures as clinically indicated
AST / ALT elevation or Increased bilirubin	Grade 3	Hold until improved to grade 1; Decrease future doses by 50%	Hold	Hold	Advise evaluation for other possible etiologies; consider imaging
Vomiting	Grade 3	Hold until resolved to grade 1; Decrease future doses by 50%	Hold	Hold	
Neuropathy	Grade 2 or greater	Hold until decreased to patient's baseline; Decrease future doses by 50%	None	None	
Depression or other clinically relevant mood disorder	Grade 3	Permanently discontinue; appropriate supportive care/intervention	None	None	
Neutropenia	Grade 3 or greater	Hold until ANC > 1000; Decrease future doses by 50%	Hold	Hold	
Hemorrhage	Grade 2 or greater	None	None	Permanently discontinue	
Myocardial infarction or other arterial thrombotic event	Grade 2 or greater	None	None	Permanently discontinue	

PROTOCOL TITLE: Phase 2A Study Evaluating a Chemokine-Modulatory Regimen in Patients with Colorectal Cancer Metastatic to the Liver

Treatment-related AEs	Toxicity grade or conditions (CTCAE5.0)	Action taken for Interferon Alpha-2b	Action taken for Rintatolimod	Action taken for Celecoxib	Additional actions

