All other clinically significant AEs ¹	Intolerable Grade 2 or Grade 3	Hold therapy until resolved; reduce future doses by 50%	Hold therapy until resolved; reduce future doses by 50%	Hold therapy until resolved	
	Grade 4	Permanently Discontinue	Permanently Discontinue	Permanently Discontinue	
1. Holding of any therapies here for intolerable grade 2 or grade 3 toxicities will be at the discretion of the investigator based upon the nature of the AE and whether one drug can be clearly implicated or not; in the case that one drug can be clearly implicated, only that drug should be dose reduced in the future; in the case that the causative agent is unclear, it is recommended that interferon and rintatolimod are reduced as directed					

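### Section 10.2.1 continues interferon and rintatolimod after celecoxib-related non-hematologic events with no grade limit, contradicting the grade 4 stop in Section 10.2

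*Combined protocol and SAP*

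**What the plan says.** Section 10.2.1 covers non-hematologic toxicity linked to celecoxib: "Considered to be possibly, probably, or definitely related to Celecoxib (Interferon Alpha-2b and rintatolimod will be continued". It then refers the reader to Table 2. Its one grade threshold, grade 2 or above, decides when celecoxib is stopped, and that stop has an exemption: "except for nausea, vomiting, or a similar readily manageable condition". No threshold governs the other two drugs.

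The parent section, 10.2, is general: "Therapy will be immediately discontinued for any grade IV treatment-related toxicity that becomes apparent". It names one exemption: "The exception to this is for grade 4 neutropenia" lasting under seven days. It also has a sentence on grade III toxicity, under which treatment is withheld and resumes once the toxicity has reversed.

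Table 2 in 10.2 (toxicity management) sets actions drug by drug. The grade 4 line for all other clinically significant events reads "Permanently Discontinue" under each of the three drugs. The hemorrhage and arterial thrombotic event rows cover grade 2 upward; they end celecoxib and list no action for interferon or rintatolimod. The neuropathy row, also grade 2 upward, holds and halves interferon and lists no action for rintatolimod. Several grade 3 rows hold all three drugs. For vomiting, the interferon entry is "Hold until resolved to grade 1; Decrease future doses by 50" percent.

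Section 10.2.2 holds the dose at grade 3 and stops treatment at grade 4 for events at least possibly related to interferon and rintatolimod.

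**The concern.** A team facing a grade 4 non-hematologic event that it attributes to celecoxib looks first at the section written for that case. That section tells it to keep giving the other two drugs. The parent section tells it to stop. Nothing says which instruction prevails, and they cannot both be followed.

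What is at stake is patient safety after the most severe non-fatal toxicities. The plan treats these events as important elsewhere: Section 10.2.3 singles out grade 4 or greater treatment-related non-hematologic toxicity for monitoring, and Section 19.4 counts it toward suspending the trial. A patient could therefore add to the suspension count while 10.2.1, read alone, calls for further doses of two drugs.

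**Working it through.** The plan states no figure on this point, so the check sets the rules side by side.

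**1. Grade 4 events attributed to celecoxib alone**

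| Event | 10.2.1: interferon and rintatolimod | 10.2 | Table 2: interferon and rintatolimod |
|---|---|---|---|
| Kidney failure, or any event without its own row | continue both | stop | stop both permanently |
| Myocardial infarction or other arterial event | continue both | stop | no action on either |
| Hemorrhage | continue both | stop | no action on either |
| Neuropathy | continue both | stop | interferon held, then halved; rintatolimod no action |

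In the first line, 10.2.1 stands against both other sources. In the other three, Table 2 itself departs from 10.2, so following the pointer to Table 2 does not restore the grade 4 stop.

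**2. Do other provisions catch these events?**

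- Section 10.2.2 does not apply when neither interferon nor rintatolimod is implicated.
- Footnote 1 of Table 2 gives the investigator discretion at intolerable grade 2 or grade 3 only.
- The laboratory check before each three-day block (10.1.1) sets limits for ANC, bilirubin and AST/ALT. It sets none for creatinine.
- Sole attribution to celecoxib is plausible. Section 13.1 discusses heart attack and lists bleeding ulcer and kidney failure for celecoxib. Section 13.2 does not name heart attack or kidney failure for interferon, and Section 13.3 reports no dose-limiting renal toxicity for rintatolimod. Bleeding is less clear-cut, because 13.2 links interferon to lowered platelets.

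**3. Doses at issue (illustration, upper bound)**

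Dosing days are 1, 2, 3, 8, 9, 10, 15, 16 and 17, which is 9 doses of each drug, at 20 million units/m² of interferon and 200 mg of rintatolimod per dose.

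- Event found before dosing on Day 8: 6 of 9 doses remain. 6 × 20 = 120 million units/m²; 6 × 200 = 1,200 mg.
- Event found before dosing on Day 15: 3 of 9 remain. 3 × 20 = 60 million units/m²; 3 × 200 = 600 mg.
- Under 10.2: 0 remain in either case.

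**4. Below grade 4**

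Table 2 has 11 action rows. Leaving out neutropenia, 10 are non-hematologic:

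- action required on both drugs, 4 (grade 3 pancreatitis, grade 3 AST/ALT or bilirubin, grade 3 vomiting, and the grade 4 catch-all already counted above);
- action required on interferon only, 2 (neuropathy, depression);
- no action on either, 3 (chills/fever, hemorrhage, arterial events);
- discretionary under footnote 1, 1 (other intolerable grade 2 or grade 3).

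4 + 2 + 3 + 1 = 10. So 6 of 10 rows differ from 10.2.1 on paper, or 7 of 10 if the discretionary row is counted. Few of the rows below grade 4 matter for celecoxib-only events. Section 13.2 lists vomiting, pancreatitis, depression and numbness or tingling for interferon, so 10.2.2 would usually apply. Liver tests are largely caught by the 10.1.1 check.

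**The case against.** The best defence is that 10.2.1 sits inside 10.2, whose grade IV rule covers any treatment-related toxicity and names a single exemption. Nothing in 10.2.1 claims to create a second. On that reading the parenthesis means only that stopping celecoxib is not in itself a reason to drop the other two drugs. That fits footnote 1 and the hemorrhage and arterial rows. A careful team could also stop for unacceptable toxicity (10.4) or on investigator judgment (12.1).

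This reading is workable and lowers the chance of harm, but it is not written down. The rows it draws support from list no action on interferon or rintatolimod at grade 4, which is what 10.2 rules out.

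Three stronger readings are tempting, and the documents do not support them:

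- A reader might infer that grade 3 vomiting is left with no action on any drug. But 10.2.1 refers to Table 2, which holds all three. An exemption from discontinuing celecoxib is compatible with a hold, and vomiting is also a listed interferon effect, which would usually bring in 10.2.2.
- A reader might take 6 of 10 rows as the measure of the problem. The count is right, but most of those rows have little relevance to events caused by celecoxib alone.
- A reader might infer that patients will be treated through grade 4 toxicity. That depends on which text the team follows, and no event rate is given.

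**Conclusion.** The point holds at grade 4. As written, 10.2.1 has no grade limit for interferon and rintatolimod. It contradicts 10.2 and the Table 2 catch-all, and Table 2 cannot act as tie-breaker because three of its rows also clash with 10.2. The practical reach is narrow: mainly grade 4 non-hematologic events attributed to celecoxib alone. Below grade 4 the conflict is largely one of wording.

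The dose figures assume that 10.2.1 is followed literally and that no other stopping reason is used, so they are an upper bound for one patient. The conclusion also takes therapy in 10.2 to mean the three-drug regimen, as the catch-all row suggests. If it meant only the implicated drug, the clash with the hemorrhage, arterial and neuropathy rows would fall away, but the clash between 10.2.1 and the catch-all row would remain. The missing grade limit is certain; its consequence is not quantifiable from the documents. The sponsor should correct it, because the rule concerns safety and the change is small.

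**What to change.** Replace the parenthesis in 10.2.1 with:

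> Interferon Alpha-2b and rintatolimod will each be continued only if the event is attributed to celecoxib alone, is below grade 4, and Table 2 does not require that drug to be held, reduced or discontinued. For any grade 4 treatment-related non-hematologic event, the 10.2 discontinuation rule prevails over 10.2.1 and Table 2, including for hemorrhage, arterial thrombotic events and neuropathy. Below grade 4, Table 2 prevails over 10.2.1 and over the general grade III withholding sentence in 10.2 where a named row applies; 10.2.2 applies to events also attributed to interferon or rintatolimod.

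The celecoxib stop rule stays as it is. The last sentence is needed because the grade III sentence in 10.2 withholds treatment, while Table 2 lists no action on interferon or rintatolimod for grade 3 hemorrhage or arterial events. If the sponsor would rather withhold both drugs there, the ranking can be reversed, but it should be stated.

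The cost is one paragraph in the next amendment, with no added procedures, visits or patients.

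### For several grade 2 or 3 non-hematologic events, section 10.2.1 discontinues celecoxib while Table 2 in section 10.2 holds it or takes no action, and neither text is said to govern

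*Combined protocol and SAP*

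**What the plan says.** Three texts in the combined protocol and SAP bear on celecoxib after an adverse event.

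- **Section 10.2.1** sets its scope as "Considered to be possibly, probably, or definitely related to Celecoxib (Interferon Alpha-2b and rintatolimod will be continued). See Table 2". Its heading limits it to non-hematologic toxicity. The rule is that "Celecoxib will be discontinued for any attributable grade" 2 or above, "except for nausea, vomiting, or a similar readily manageable condition".
- **Table 2 in section 10.2** (the toxicity management table, not the reporting table of the same number in section 17.2) has its own celecoxib column. The row "AST / ALT elevation or Increased bilirubin" at grade 3 gives a hold, as does grade 3 pancreatitis. The catch-all row, triggered at "Intolerable Grade 2 or Grade 3", gives "Hold therapy until resolved". Its footnote adds: "Holding of any therapies here for intolerable grade 2 or grade 3 toxicities will be at the discretion of the investigator". Neuropathy of grade 2 or more and grade 3 depression carry no celecoxib action. Hemorrhage and "Myocardial infarction or other arterial thrombotic event", both at grade 2 or greater, stop celecoxib permanently, and so does grade 4 in the catch-all row.
- **The running text of section 10.2** says study treatment resumes after a grade 3 treatment-related toxicity has reversed, and stops if it persists.

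**The concern.** Section 10.2.1 sends the reader to Table 2 and then states a rule that departs from it. An investigator with a grade 3 transaminase rise that might be due to celecoxib finds an instruction to discontinue in one place and to hold in another. For a neuropathy judged possibly related to celecoxib, one text stops the drug and the other leaves it alone.

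Two things are at stake. The first is patient safety: the protocol gives incompatible instructions for one event. The second is uniform delivery of a three-drug regimen in a study of about 15 patients, 12 of them evaluable (section 4), where a few differently handled cases would make the regimen harder to describe.

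The events are foreseeable. Section 13.1 lists liver effects of celecoxib, and section 10.2.3 reports 13.9% grade 3 and 4 hepatotoxicity with high-dose interferon in an earlier melanoma trial. That trial used a different regimen and schedule, so the figure is not a forecast for this one.

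**Working it through.** The plan has no figure to reproduce here. The check sets the celecoxib column of Table 2 beside section 10.2.1, row by row, for an event at least possibly related to celecoxib.

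| Event and grade in Table 2 | Section 10.2.1 | Table 2, celecoxib | Result |
|---|---|---|---|
| Pancreatitis, 3 | discontinue | hold | conflict |
| AST/ALT or bilirubin, 3 | discontinue | hold | conflict |
| Other clinically significant, intolerable 2 or 3, not readily manageable | discontinue | hold until resolved | conflict |
| Neuropathy, 2 or more | discontinue | none | conflict |
| Depression or mood disorder, 3 | discontinue | none | conflict |
| Chills/fever, 3 | discontinue unless readily manageable | none | depends on the exception |
| Vomiting, 3 | excepted | hold | outside the discontinuation rule |
| Neutropenia, 3 or more | hematologic, not covered | hold | outside the rule |
| Hemorrhage, 2 or more | discontinue | permanent stop | agree |
| Arterial thrombotic event, 2 or more | discontinue | permanent stop | agree |
| Other clinically significant, 4 | discontinue | permanent stop | agree on celecoxib |

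Of 11 entries, 5 conflict, 1 depends on how the exception is read, 2 lie outside the rule and 3 agree (5 + 1 + 2 + 3 = 11).

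**Are hold and discontinue different actions here?** Yes. Table 2 keeps holding apart from permanent discontinuation, and section 10.2.2 keeps a dose that is held and restarted apart from treatment that is discontinued.

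**Do the scopes overlap?** Yes. Table 2 deals with treatment-related events, and section 10.2.1 with events at least possibly related to celecoxib. The three drugs are given on the same days, so one event can be possibly related to more than one of them and fall under both texts.

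**The other two drugs.** Section 10.2.1 continues interferon and rintatolimod. Table 2 holds both in the pancreatitis and liver-test rows and in the catch-all row (there subject to the footnote). It also holds interferon for neuropathy, stops interferon for grade 3 depression, and stops all three drugs at grade 4 in the catch-all row.

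**How much celecoxib could turn on this.** The schedule has 3 courses × 3 days = 9 dosing days, or 9 × 2 = 18 doses. In the hold rows both texts interrupt celecoxib when the event occurs and can differ only on resumption. For an event after the first course, at most 9 − 3 = 6 dosing days (12 doses) are affected; after the second, 9 − 6 = 3 days (6 doses); after day 17, none.

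**The case against.** The strongest defence is that Table 2 is the general guide for a three-drug regimen and section 10.2.1 a stricter rule for one drug, so the specific text prevails. That is a plausible reading, but the protocol does not state it. Table 2 has its own celecoxib column, and section 10.2.1 refers to the table without saying that it overrides it. The catch-all footnote does not settle the matter either. It gives discretion over holding in that row only, and where one drug is clearly implicated it provides for reducing that drug's dose, not for stopping celecoxib.

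Other parts of the defence stand and limit the point:

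- A reader might infer that Table 2 only ever holds celecoxib. It does not; three entries stop it permanently.
- A reader might infer that every attributable grade 2 or 3 event is affected. The exception covers more than nausea and vomiting. For a tolerable grade 2 event with no row of its own, Table 2 is silent and section 10.2.1 simply applies.
- Section 10.2.1 does not say that the stop is permanent. That is a reasonable inference from the protocol's vocabulary, but still an inference.
- The celecoxib cells for pancreatitis and liver tests give no restart condition. Resumption rests on the catch-all row and the grade 3 sentence in section 10.2.

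**Conclusion.** The contradiction is real and confined to identifiable rows. Discontinuation is set against a hold for grade 3 pancreatitis, grade 3 liver-test elevation, and other clinically significant events at intolerable grade 2 or grade 3 that are not readily manageable. It is set against no action for neuropathy of grade 2 or more and grade 3 depression. The handling of interferon and rintatolimod is inconsistent as well. This assumes the event is judged at least possibly related to celecoxib and that discontinuing is not the same as holding, as the protocol's own usage indicates.

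A reader might go further and conclude that the second biopsy, and with it the primary result, is compromised. The documents do not support that. The primary analysis cohort needs only paired pre- and post-treatment measurements (section 19.2), and section 11.1.5 still collects the biopsy after incomplete treatment unless safety overrides. The documents give no frequency for the conflicting events. This is an internal inconsistency that bears on safety instructions and consistent conduct, not a demonstrated flaw in the primary analysis.

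**What to change.** Reconcile the running text of section 10.2, Table 2 with its footnote, and section 10.2.1. State one action per event and grade for each of the three drugs, say which text governs where two could apply, and give the resumption condition wherever a hold is intended. Clarify which conditions count as readily manageable, so that the chills/fever row can be placed. The clinical team decides which action applies; this review takes no position on that. The cost is protocol amendment wording, with no change to sample size, endpoints or analysis.

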10.2.2 Interferon Alpha-2b and/or rintatolimod Non-hematologic toxicities

Considered to be possibly, probably, or definitely related to Interferon Alpha-2b and rintatolimod:

- Interferon Alpha-2b :

For grade 3 toxicity:

- 1st episode: dose will be held and restarted at the next study visit at a dose reduction of 50%. The dose can be re-escalated if toxicity is reduced to \leq grade 1 or baseline.
- 2nd episode: Treatment will be discontinued

For grade 4 toxicity (except neutropenia of < 7 days duration):

- Treatment will be discontinued

- Rintatolimod:

For grade 3 toxicity:

- 1st episode: dose will be held and restarted at the next study visit at a dose reduction of 33%. The dose can be re-escalated if toxicity is reduced to \leq grade 1 or baseline
- 2nd episode: dose will be held and (if toxicity is resolved to \leq grade 1 or baseline) restarted at the next study visit at a dose reduction of 33%. The dose cannot be re-escalated

PROTOCOL TITLE: Phase 2A Study Evaluating a Chemokine-Modulatory Regimen in Patients with Colorectal Cancer Metastatic to the Liver

For grade 4 toxicity:

- Treatment will be discontinued

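### Sections 10.2 and 10.2.2 contradict Table 2 on three kinds of related grade 3 event, including whether interferon may restart after depression, and nothing says which rule governs

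*Combined protocol and SAP*

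**What the plan says.** Section 10.2 sets out its dose rules together and does not rank them. Its text has two general rules. At grade 4: "Therapy will be immediately discontinued for any grade IV treatment-related toxicity that becomes apparent", with short-lived neutropenia excepted. At grade 3: "Study treatment will be reinitiated for any grade treatment-related III toxicity pending the reversal of such toxicity", where reversal means return to the subject's own baseline. Treatment is discontinued if the toxicity persists.

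Table 2 in the same section (toxicity management, not the adverse event reporting table in 17.2 that carries the same number) gives actions by event:

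- Grade 3 depression or mood disorder, interferon column: "Permanently discontinue; appropriate supportive care/intervention". The other two drugs are unchanged.
- Grade 3 chills/fever: no action for any of the three drugs. The additional-actions column reads "Consider additional acetaminophen dosing, supportive care".
- Catch-all row (intolerable grade 2, or grade 3), interferon and rintatolimod alike: "Hold therapy until resolved; reduce future doses by 50" percent.

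Section 10.2.2 covers non-hematologic events at least possibly related to interferon and/or rintatolimod. At grade 3 it says for interferon "1st episode: dose will be held and restarted at the next study visit at a dose reduction of 50" percent, and for rintatolimod "1st episode: dose will be held and restarted at the next study visit at a dose reduction of 33" percent. Both may be re-escalated once the toxicity is down to grade 1 or baseline. A second grade 3 episode stops interferon. For rintatolimod it means another hold and a restart at a 33% reduction without re-escalation.

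Section 10.2.1, on celecoxib, refers the reader to Table 2. Section 10.2.2 does not.

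**The concern.** A pharmacist or covering clinician has to turn these rules into an order within days, and for three kinds of event the rules give different orders. Depression matters most, because one rule bars further interferon and two others bring it back. It is also foreseeable: Section 13.2 lists depression that can be severe among the risks of prolonged interferon. Section 19.4 leaves grade 3 depression lasting under 7 days out of the events counted toward study suspension. For such an event the patient-level dosing rule is therefore the main written protection, and that rule is contradictory.

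Chills/fever is less dangerous but may arise more often. Section 10.2.3 reports 48.2% grade 3 and 4 constitutional toxicity in the cited melanoma trial of high-dose interferon. That trial gave 5 × 4 = 20 daily doses against 9 here, and its category also includes fatigue and malaise, so the figure shows only that the event is not rare. It is not a forecast for this study.

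**Working it through.** The plan gives no figure to reproduce. The check sets the rules side by side and applies the stated percentages.

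**Inputs.** Table 1: interferon 20 million units/m² per dose, rintatolimod 200 mg per dose. Reductions are those in Table 2 and 10.2.2.

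**Step 1: do the scopes overlap?** Table 2 is headed for treatment-related events. Section 10.2.2 takes non-hematologic events at least possibly related to interferon and/or rintatolimod. Depression and chills/fever are non-hematologic and 10.2.2 excludes no event, so a related grade 3 case falls under both.

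**Step 2: what does each rule order at a first related grade 3 episode?**

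| Event | Table 2 | Section 10.2.2 | Section 10.2 text |
|---|---|---|---|
| Depression or mood disorder | Interferon 0, permanently | Interferon held, then 20 × 0.50 = 10 million units/m²; may return to 20 | Restart after return to baseline |
| Chills/fever | Interferon 20 million units/m², rintatolimod 200 mg, both unchanged | Both held, then interferon 10 million units/m² and rintatolimod 200 × 0.67 = 134 mg | Presupposes withholding, then restart |
| Event with no row of its own | Rintatolimod 200 × 0.50 = 100 mg | Rintatolimod 134 mg | Restart; no reduction stated |

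In the third row the gap is 134 − 100 = 34 mg per dose, or 34 / 200 = 17% of the full dose. Interferon is cut by 50% under both rules there, so only rintatolimod is in conflict.

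**Step 3: does any sentence rank the rules?** The opening of 10.2 does not. The pointer to Table 2 in 10.2.1 concerns celecoxib. The footnote to Table 2 belongs to the catch-all row. It leaves to the investigator whether to hold therapy and, where one drug is clearly implicated, confines the reduction to that drug. It does not choose between 50% and 33%.

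**The case against.** The best defence is that a specific row ordinarily overrides a general rule. On that reading depression stops interferon and chills/fever changes nothing, which is very probably what was meant; acetaminophen for fever in 10.2.3 points the same way. Patients are also protected elsewhere: an interval history and examination before each 3-day block (10.1.1), discontinuation on the investigator's judgment (12.1), exclusion of known serious mood disorders (3.2), and the 10.2 condition that the event must first return to baseline. All of this stands, and it limits the harm. But the precedence is unwritten, the 10.2 restart sentence is worded to reach every related grade 3 event, and the safeguards permit stopping interferon without saying that Table 2 requires it. Nor does a specific-over-general reading clearly settle the rintatolimod percentage, because both the catch-all row and 10.2.2 are general rules.

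A reader might infer that the conflict runs through most of Table 2. The documents do not support that:

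- The hemorrhage and arterial rows act on celecoxib alone, and 10.2.1 continues the other two drugs after celecoxib toxicity. They conflict with 10.2.2 only if the event is attributed to interferon or rintatolimod.
- In the vomiting row the interferon entry is "Hold until resolved to grade 1; Decrease future doses by 50" percent, so the size of the cut agrees with 10.2.2. Rintatolimod is held there, and in the pancreatitis and liver rows, with no restart dose; 10.2.2 supplies one, which completes those rows and does not contradict them.
- No rintatolimod action for neuropathy or depression can be read as attributing those events to interferon, since 13.2 lists both among its risks.

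A reader might also take the 7-day limit in 19.4 as a hidden dosing rule for fever. It defines events for the suspension rule. The same list exempts short-lived depression, for which Table 2 nonetheless stops interferon, so it cannot be read across to dosing.

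**Conclusion.** The contradiction is real in three places: interferon after related grade 3 depression or mood disorder (permanent stop versus restart at 10 million units/m²), both infused drugs after related grade 3 chills/fever (no change versus hold and reduce), and rintatolimod after related grade 3 non-hematologic events without their own row (100 mg versus 134 mg). The first bears on patient safety. The other two leave the dose for a given event undefined.

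This assumes a first episode at least possibly related to the drug in question. The number of patients who would meet such an event, and any effect on the primary endpoint, cannot be derived from the documents. A reader might be drawn to calculate how much extra interferon a patient would receive after depression. That depends on when the event starts, how fast it resolves and whether the dose is re-escalated, none of which is given, so no such total is supported.

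**What to change.** Add an exception to both 10.2 and 10.2.2, along these lines:

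> *Exception: related grade 3 depression, or another mood disorder of clinical relevance, ends interferon permanently, and grade 3 chills/fever is managed with supportive care and no dose change, both as in Table 2 of Section 10.2. For all other related grade 3 non-hematologic events, the second-episode rules in 10.2.2, including the interferon stop, continue to apply, as does the grade 4 stop in 10.2.*

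A blanket statement that Table 2 governs would be the wrong repair. Its named rows contain no second-episode rule, so it could remove the interferon stop for repeat grade 3 hepatotoxicity, vomiting, pancreatitis or neuropathy.

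State one rintatolimod reduction in both the catch-all row and 10.2.2. A 50% cut matches Table 2 and the 100 mg toxicity presentation in 32.3.2, but either figure is workable: at the stated 2.5 mg/mL, 134 mg is 134 / 2.5 = 53.6 mL, so a 33% cut could be given as a partial infusion. The sponsor may choose. Because 10.2.2 uses 33% at the second episode too, that line should be reworded if 50% is adopted.

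The cost is one paragraph and one aligned percentage in an amendment, with no added visits, patients or assays.

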32.2.4 Drug administration

Interferon Alpha-2b (20 million units/M²) will be administered intravenously over 20 minutes once a day on Days 1-3, 8-10, and 15-17.

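### After a grade 3 liver-test or vomiting event, Table 2 and section 10.2.2 lead to different later interferon doses and different actions at recurrence, and no text says which governs

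*Combined protocol and SAP*

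**What the plan says.** Interferon alpha-2b is planned at 20 million units/m² and, per section 32.2.4, "will be administered intravenously over 20 minutes once a day on Days 1-3, 8-10, and 15-17", which makes nine doses. Three texts then govern it after a treatment-related grade 3 toxicity.

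- **Table 2 (section 10.2), interferon column.** For AST/ALT elevation or increased bilirubin: "Hold until improved to grade 1; Decrease future doses by 50" percent. For vomiting: "Hold until resolved to grade 1; Decrease future doses by 50" percent. For neuropathy of grade 2 or greater: "Hold until decreased to patient's baseline; Decrease future doses by 50" percent. The catch-all row for other clinically significant events has the same structure (hold until resolved, then halve), but footnote 1 leaves holding to the investigator and limits later reduction to a drug that is clearly implicated. None of these rows mentions re-escalation or a second episode.
- **Section 10.2.2, interferon bullet**, for non-hematologic grade 3 toxicity considered related: "1st episode: dose will be held and restarted at the next study visit at a dose reduction of 50" percent. Then: "The dose can be re-escalated if toxicity is reduced to" grade 1 or lower, or baseline. Then: "2nd episode: Treatment will be discontinued". (The re-escalation words also appear under rintatolimod; this point concerns interferon.)
- **General text of section 10.2:** "Study treatment will be reinitiated for any grade treatment-related III toxicity", provided that the toxicity has returned to the patient's baseline. It does not mention recurrence.

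Section 10.2.1 refers the reader to Table 2. Section 10.2.2 does not, and no section sets an order of precedence.

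**The concern.** The same event falls under two rules that agree on the first restarted dose and then part. Table 2 applies the cut to future doses without limit, while 10.2.2 lets the cut be reversed. The condition for reversal does no work for a patient restarted under the Table 2 rows above, because the recovery those rows require before restart already satisfies it. At recurrence, 10.2.2 stops interferon; Table 2 applied again would hold and re-dose, and 10.2 would restart.

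This is first a patient-safety matter. Section 10.2.3 itself reports two treatment-related deaths from hepatotoxicity in its cited melanoma trial, which used interferon at this daily dose, and the liver row is one of those in conflict. Two investigators who both follow the protocol could give materially different doses after a reversed grade 3 liver event. One could stop and the other re-dose after a second.

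It also means that exposure before the post-treatment biopsy can depend on which text was followed, in a study with 12 evaluable patients.

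**Working it through.** The plan states no figure on this point, so there is nothing to reproduce. The check sets the texts side by side and then adds up the doses.

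**Side by side, interferon, related grade 3 AST/ALT/bilirubin or vomiting**

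| Question | Table 2 | Section 10.2.2 | General text of 10.2 |
|---|---|---|---|
| Recovery needed to restart | grade 1 | none stated; next study visit | baseline |
| Dose at restart | 50% | 50% | not stated |
| May the dose rise again? | no provision; future doses are cut | yes, at grade 1 or lower, or baseline | not stated |
| Second grade 3 episode | no separate rule | discontinue | restart after any reversed grade 3 toxicity |

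Neuropathy at grade 3 and the catch-all row follow the same pattern, with recovery to baseline and until resolved respectively. The catch-all row is subject to footnote 1.

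**Inputs.** Full dose 20 million units/m² (Table 1 and 32.2.4); half dose 20 × 0.5 = 10; nine planned doses, 9 × 20 = 180.

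**First episode, six doses left.** Assume that the event follows the three week-1 doses and that all six remaining doses are eventually given.

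- Table 2, all six halved: 6 × 10 = 60.
- 10.2.2, one three-day block reduced and then re-escalated: 3 × 10 + 3 × 20 = 90.
- 10.2.2, one dose reduced and then re-escalated: 1 × 10 + 5 × 20 = 110.

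Adding the 3 × 20 = 60 already given, the course totals are 120, 150 and 170 of a planned 180. Re-escalation in 10.2.2 is permitted, not required, so an investigator who does not use it would also give 60 over the six doses.

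**Second episode, three doses left.** Assume that it follows week 2 at half dose.

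- 10.2.2: 3 × 0 = 0.
- Table 2 read as staying at half dose: 3 × 10 = 30.
- Table 2 read as halving again: 3 × 5 = 15.

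With 60 + 30 = 90 already given, the course totals are 90, 120 and 105.

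**The case against.** **The two texts can be read in sequence.** Section 10.2.2 orders a restart at half dose and only then permits re-escalation. Within that section the re-escalation condition is not idle, since no recovery grade is required for restart. This stands. A reader might infer that the cut can last zero doses, so that full dose comes next and six remaining doses total 120 million units/m². The documents do not support that: both texts make the first restarted dose a half dose, so 110 is the most that the written order allows. The later doses still differ.

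**On recurrence, Table 2 is silent rather than contradictory**, and a specific rule may fill a silence. This is a fair reading, and it makes the second-episode issue softer than the re-escalation one. But nothing says that 10.2.2 supplements the table, the table's instruction applies to any qualifying grade 3 event, and 10.2 speaks of any grade 3 toxicity. The figure of 15 rests on an interpretation that the protocol does not state.

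**Table 2 is specific to the toxicity.** A reader might infer that it halves interferon after every grade 3 event. It does not: chills/fever carries no interferon action, nor do hemorrhage and arterial thrombotic events, and grade 3 depression is a permanent stop. Pancreatitis is halved but has no recovery grade in its row, and neutropenia is hematologic and outside 10.2.2. The point is therefore confined to the rows named.

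**Other safeguards exist.** Section 10.1.1 requires examination and laboratory limits before each three-day block, and 19.4 monitors related SAEs continuously. These bear on whether a block starts and whether the study is suspended. They do not settle the interferon dose.

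**The effect on the biopsy endpoint is not quantified.** Correct. Evaluability requires only paired values, and no planned analysis uses interferon exposure. This consequence is secondary.

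**Conclusion.** The conflict is real in the current text for related grade 3 AST/ALT/bilirubin elevation and vomiting, and similarly for grade 3 neuropathy and, subject to footnote 1, the catch-all row. After a first episode with six doses left, later interferon is 60 million units/m² under Table 2, against 90 to 110 if re-escalated under 10.2.2. After a second episode with three doses left, it is 0 under 10.2.2, against 30 or, on the less explicit reading, 15. These figures rest on the assumed event times and on all remaining doses being given unless interferon is stopped. Other timings change the totals but not the disagreement.

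How many patients would meet the conflict cannot be derived from the documents. A reader might apply the 13.9% hepatotoxicity rate in 10.2.3 to 15 patients and get 15 × 0.139 = 2.1. That rate combines grades 3 and 4, and grade 4 events lead to discontinuation under both texts. It also comes from a schedule of 5 × 4 = 20 doses rather than nine. It does not give a count for this trial, and the contradiction does not depend on one.

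Nor do the overlapping conditions show that the re-escalation condition has to differ from the restart condition. That would be a clinical rule, and the documents establish only that the texts disagree.

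**What to change.** Reconcile Table 2, the general text of 10.2 and section 10.2.2 in one amendment, so that all three give the same answer to two questions:

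1. whether an interferon dose reduced after a grade 3 toxicity may be re-escalated and, if so, when;
2. what happens to interferon at a second grade 3 episode.

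State which text takes precedence where a Table 2 row and 10.2.2 both apply. The answers may differ by toxicity row if that is intended, but they should then be written in the row. The sponsor chooses the rules.

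The cost is protocol wording in a single amendment. It adds no procedures or visits and does not change the sample size.
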